4.6 Surgical Extractions

All surgeries will be performed by qualified clinicians in an appropriately equipped surgical operatory located in the Periodontal Clinic at UAB School of Dentistry.

Prior to extraction surgery, participants will be given a loading dose of antibiotics based on their medical history and concomitant medications. A suggested prophylactic regimen follows:

2 gm of Amoxicillin 1 hour prior to the procedure followed by 500mg (TID) for 7 days

Patients with reported allergy to Amoxicillin:

600mg Clindamycin 1 hour prior to the procedure followed by 300mg (TID) for 7 days

The facial area will be scrubbed and the oral cavity disinfected by rinsing for 1 minute with a (0.12% chlorhexidine gluconate) antimicrobial oral rinse. Prior to extractions clinical photographs will be taken from the buccal and occlusal aspects. Photographs will be taken in a 1:1 ratio using a Nikon D-70 camera with a sunpack ringflash.

After preparation and isolation of the surgical area, anesthesia will be achieved in the region by regional block or local infiltration. Conscious sedation may be added at the surgeon's discretion to help manage patient anxiety.

The teeth will be extracted as atraumatically as possible, without raising a flap, utilizing periotomes and the Easy Extrac system. Grafting procedures will include the use of FDBA and collagen plugs in all experimental groups. In all groups, the integrity of the remaining socket walls will be assessed and measurements recorded on the surgical CRF. The sockets will be debrided and a bleeding surface created by decorticating the socket walls with either a curette or a surgical round burr.

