12.4 Statistical Analysis

The general approach to statistical analysis of the study aims will be based on mixed-model analysis of variance (ANOVA). This approach will accommodate the inclusion of correlated observations due to study subjects potentially contributing measurements of more than one single tooth site to the analysis.

The sample distributions will be examined for each outcome variable. If these distributions depart substantially from normality, transformations of the data will be evaluated. If normality cannot be established by transformation, rank-based analyses will be used.

Subjects will be included as a random effect on the analyses that include multiple observations per subject. For analysis of histological data, only one tooth site per subject will be evaluated and the model will not include a random effect.

Smoking status will be included in all models in order to account for differences in response between smokers and non-smokers, and so that the analysis will correspond to the study's randomization strategy. Comparisons between smokers and non-smokers are not a primary interest in the study.

For aims in which interaction terms are of interest, significant interaction terms will be investigated using plots of least square means and separate post-hoc analyses for individual time points.

Hypothesis 1

Differences among the four groups will be evaluated by the overall F-test for the ANOVA. Pairwise comparisons among group means will be conducted using Tukey's test. Contrasts will be constructed to address each specific aim (SA).

SA-1: Compare alveolar ridge dimensions in grafted extraction sockets to that of sites healed without grafts after 8 weeks of post-extraction healing.

This SA will be addressed by comparing the combined mean of the three graft groups (FDBA/TCP, DDBA/TCP/PRP, FDBA/TCP/PDGF) with that of the CONTROL group by calculating a contrast and the corresponding F-test. Pairwise comparisons among means will be conducted using Tukey's test..

Hypothesis II

The addition of growth factors to bone grafting materials will enhance osseous and soft tissue healing.

SA-2: Assess the efficacy of bone grafting with and without enrichment with growth factors to preserve the volume of bone in extraction sockets.

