This SA will be addressed using mixed-model ANOVA to compare mean bone volume among the four groups. Post-hoc pairwise comparisons will use Tukey's test. The effect of growth factors enrichment will be addressed using contrasts and F-tests to compare the mean of Group-4 with those of each of the other groups. If there is not a significant difference among the group means of Groups 1-3, the combined mean of these three groups will be compared with that of Group-4.

SA-3: Compare soft tissue healing between groups at week-1, week-2, week-4 and after 8 weeks of healing.

The analysis of SA-3 will be mixed-model ANOVA including measurements of healing made at each time points. Time will be included in the model in order to account for unequal spacing of the observational times. The statistical test that will be of primary interest will be the F-test for Group by time interaction.

SA-4: Assess quantitative bone fill across groups after 8 weeks post-extraction healing.

Qualitative bone fill will be compared among four groups using mixed-model ANOVA and the 8 week measurement only. Post-hoc pairwise comparisons will use Tukey's test.

SA-5: Compare qualitative bone fill across groups after 8 weeks post-extraction healing.

Percent new bone, percent residual graft, and percent soft-tissue will be compared among the four groups using ANOVA. For this analysis, there will be a single measurement of each of the variables per participant, so correlated observations will not be an issue in the analysis. Post-hoc pairwise comparisons will use Tukey's test.

SA-6: Assess the relationship of osseous healing and implant stability at insertion across groups after 8 weeks post-extraction healing.

This SA will be addressed by including the implant stability measure as a predictor variable in the analysis of osseous healing. The statistical test that will be of primary interest for this analysis will be the two-factor interaction of stability and group.

Hypothesis III

Laser thread-textured (LTT) dental implant will preserve longitudinal peri-implant crestal bone more effectively than implants with Resorbable blast texturing (RBT).

SA-7: Assess the efficacy of LTT and RBT surface topographies when surgically implanted into extraction sockets.

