A conservative approach to power estimation was used, assuming an effective sample size of 25 observations per extraction-implant group. Power calculations utilized the Power and Precision, release 2.00, (Borenstein, 2000) and nQuery Advisor 6.0 (Janet D. Elashoff, 1995-2005) software packages. Power to detect a “medium” effect size, corresponding to a difference between group means equal to 0.50 times the within-group standard deviation (sd) was calculated. Also, the effect size detectable with 80% power was calculated. All power estimates were based on two-sided testing at the 95% confidence level.

The power for SA-1 is largely determined by the size of control group, since the primary comparison is equivalent to a t-test of the mean of the controls vs others. Thus, the assumed effective sample sizes of 25 and 75 would yield approximatey 57% power to detect a medium effect size. The difference detectable with 80% power would be approximately 0.65sd .

Power for SA-2, SA-4 and SA-5 was based on a one-way ANOVA model. The proposed sample size would provide 52% power to detect a medium effect size or 80% power to detect an effect size equivalent to a two-group difference of 0.34sd . These approximations also apply to SA-3, with the appropriate sd being the within-group standard deviation of the changes across the observation times.

The total sample size for SA-5 would be 80, or 20 per group, since this SA is based on histology, with a single extraction per participant. Power to detect a medium effect size would be 42%. The effect size detectable with 80% power is equivalent to a two-group difference of 0.72sd.

Power for SA-6 was based on linear regression with a four-category dummy variable. If stability and group each explain 10% of the observed variance, the proposed sample size would provide 80% power to detect an increment of 8.6% in explained variance for the stability*group interaction.

Power for comparison of rates of infection signs for SA-7 was based on the chi-square test for the odds ratio. The proportions in the two groups were centered on 0.50, in order to provide a conservative estimate of power. The effective sample size of 50 per group would provide 80% power to detect an odds ratio of approximately 3.2 for the association between implant type and infection.

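### SA-3's only named primary test, group by time, cannot detect a group difference that is constant from week 1 to week 8; secondarily, SA-1 could use socket-wall distances already recorded

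*Combined protocol and SAP*

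**What the plan says.** **SA-3.** The aim (Sections 2.3 and 12.4) is a between-group comparison of soft-tissue healing at weeks 1, 2, 4 and 8. The analysis is a mixed-model ANOVA with time in the model, and one test is singled out: "The statistical test that will be of primary interest will be the F-test for Group by time interaction". The general text of 12.4 adds that, where interactions are of interest, "significant interaction terms will be investigated using plots of least square means and separate post-hoc analyses for individual time points". Section 12.5 carries its one-way ANOVA power over to SA-3, with "the appropriate sd being the within-group standard deviation of the changes across the observation times". An overall F-test among the four groups, Tukey comparisons, and contrasts for every specific aim are also mentioned, in a paragraph placed under Hypothesis 1.

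**SA-1.** The analysis is described so: "This SA will be addressed by comparing the combined mean of the three graft groups" with that of control, at 8 weeks. The one covariate named for every model is smoking: "Smoking status will be included in all models in order to account for differences in response between smokers and non-smokers". Section 12.5 says "the primary comparison is equivalent to a t-test of the mean of the controls vs others". Section 4.6 states: "In all groups, the integrity of the remaining socket walls will be assessed and measurements recorded on the surgical CRF"; item 4.8-1 lists the mesio-distal and bucco-lingual distances. No model in 12.4 uses them.

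**The concern.** In SA-3, a group-by-time test asks whether the differences between groups change from visit to visit. It does not ask whether the groups differ. All four visits follow treatment, so a graft that heals better by week 1 and stays better by the same amount answers the aim but produces no interaction. The per-visit comparisons that the aim describes are tied to a significant interaction, so they would not be reached either. A real and lasting benefit could be reported as a null primary result for SA-3.

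In SA-1, the test of Hypothesis I is planned at about 57% power for 0.50 sd, while measurements of starting socket size, which may explain part of the outcome variance, are collected and left unused. That costs some precision and leaves chance imbalance in starting size uncorrected.

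**Working it through.** **Inputs from Section 12.5:** two-sided alpha 0.05; difference 0.50 sd; effective n 25 per extraction group (25 versus 75 for SA-1). **Assumed, because the documents do not give them:** between-visit correlation r = 0.7 / 0.5 / 0.3 with equal variances and correlations; correlation rho between socket distance and the SA-1 response.

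**1. The plan's own figures.**
- SA-3 (one-way ANOVA): effect size f = 0.25 and N = 100 give noncentrality 100 × 0.25² = 6.25. F on 3 and 96 df gives 52%, as stated.
- SA-1 (t-test, 98 df): noncentrality 0.50 × √(25 × 75/100) = 2.165 gives 57.3%, against about 57% stated.

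**2. SA-3, difference of 0.50 sd at every visit.**
- *Interaction.* Every group-by-visit deviation is zero, so the noncentrality is zero and power equals alpha, 5%. This holds for categorical time (9 df) and for numeric time (3 df, equal slopes).
- *Group main effect.* The variance of a subject's four-visit mean is (1 + 3r)/4 = 0.775 / 0.625 / 0.475. For control versus three grafts the deviations are −0.375 and three times +0.125, with sum of squares 0.1875. Noncentrality is 25 × 0.1875 / variance = 6.05 / 7.50 / 9.87. For two groups versus two it is 25 × 0.25 / variance = 8.06 / 10.0 / 13.2. Power is from F on 3 and 96 df.
- *Holm on both tests.* At least one is significant if either p-value is below 0.025. The two tests are independent in this balanced layout, so power is 1 − (1 − main-effect power at 0.025) × 0.975. For control versus three grafts at r = 0.7: 1 − 0.61 × 0.975 = 0.405.

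| Constant difference, r = 0.7 / 0.5 / 0.3 | Interaction | Main effect | Holm pair |
|---|---|---|---|
| Control vs three grafts | 5 / 5 / 5% | 50 / 60 / 74% | 40 / 50 / 64% |
| Two vs two | 5 / 5 / 5% | 64 / 74 / 86% | 54 / 65 / 79% |

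**3. SA-3, what the fix costs.** Take 0.50 sd at weeks 1 and 2 and none at weeks 4 and 8, with categorical time. For control versus three grafts the interaction noncentrality is 25 × 0.75 × 0.25 / (1 − r) = 15.6 / 9.4 / 6.7.

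| Early difference only, r = 0.7 / 0.5 / 0.3 | Interaction alone | Holm pair | Main effect alone |
|---|---|---|---|
| Control vs three grafts | 78 / 52 / 37% | 72 / 47 / 37% | 15 / 18 / 22% |
| Two vs two | 91 / 67 / 49% | 87 / 62 / 50% | 19 / 22 / 29% |

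The largest loss is about 6 points. The last column shows why the main effect should not replace the interaction.

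**4. SA-1 with two covariates.** Noncentrality becomes 2.165 / √(1 − rho²), on 96 df.

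| Assumed rho | 0 | 0.1 | 0.2 | 0.3 | 0.5 |
|---|---|---|---|---|---|
| Power at 0.50 sd | 57% | 58% | 59% | 61% | 70% |

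**The case against.** **A group test may already be planned.** Hypothesis I has a single aim, so the sentence promising contrasts for every aim reads naturally as wider than its heading, and the overall F-test and Tukey sentences stand beside it. A mixed model would normally contain a group term, and being of primary interest does not mean being the only test. A reader might therefore infer too much by concluding that SA-3 has no test of group differences at all; the documents do not support that. What stands is that the group effect has no stated role beside the interaction in SA-3 and no multiplicity rule.

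**The interaction was intended.** Section 12.5 sizes SA-3 on changes across visits, so the choice is consistent within the power section. It still does not match the wording of the aim.

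**Time may be numeric.** Section 12.4 brings in time to handle unequal spacing, which suggests a 3-df interaction. That helps for some patterns: for a linear decline to zero at week 8 (two versus two), power is 84 / 61 / 45%, against 66 / 40 / 29% with categorical time. It changes nothing for a constant difference.

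**A day-0 value exists.** Wound distances after suturing are recorded (4.8-3). As a time-0 level they could let the interaction see a difference that arises before week 1, but SA-3 lists only weeks 1, 2, 4 and 8.

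**SA-1.** This objection largely succeeds against any claim of error. Item 4.8-1 gives no timing; the order of 4.6 and 4.7 only implies that the distances precede grafting. They are socket distances, not an earlier reading of the ridge outcome. SA-1 does not say whether its response is the probe measure of Section 5.3 or a CBCT measure, and the synopsis outcome of changes over time leaves a change score possible. Nor does the reproduced 57% prove that baseline is ignored, since the sd in 12.5 could be that of a change.

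**Conclusion.** The SA-3 point holds as an inexpensive improvement worth making. For a difference constant from week 1 to week 8, the one named primary test has 5% power under either coding of time, and the interaction-dependent per-visit analyses do not rescue it. A group main effect would have 50 / 60 / 74% power for control versus three grafts, or 64 / 74 / 86% for two versus two. These figures assume 0.50 sd, 25 per group, equal between-visit correlations of 0.7 / 0.5 / 0.3, and no further allowance for sites clustered within subjects.

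The SA-1 point is secondary: an available gain in precision, not an error. A reader might infer that the unadjusted contrast is biased; it is not, because assignment is randomized. The gain is negligible at rho of 0.1 to 0.2, reaches 70% power only at rho of 0.5, and may be smaller if the response is already a change score. The documents give no value for rho.

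**What to change.** **SA-3.**
- Keep the group-by-time test and state whether time is categorical or numeric.
- Prespecify the 3-df group main effect over visits, with Holm across the two tests.
- Prespecify group contrasts at each visit, with Holm over the four visits, and report them whether or not the interaction is significant.

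**SA-1.**
- Add the mesio-distal and bucco-lingual socket-wall distances as covariates.
- State that they are taken before grafting, and name the ridge measurement that is the response.
- Do not adjust for fill, volume or density from the first CBCT: Section 8.1 places that scan after grafting, so these values can carry the treatment effect.

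**Cost.** SAP wording on data already scheduled for collection. SA-3 gives up at most about 6 points of power for a purely early difference with categorical time. SA-1 spends 2 df, and power stays at 57% if the covariates turn out to be uninformative.

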1.2 Platelet Rich Plasma

The addition of platelet rich plasma (PRP) to graft materials is gaining clinical acceptance as an added stimulus to wound healing in both osseous and soft tissues. PRP, an autologous concentration of human platelets in a small volume of plasma, consists of growth factors derived from platelets degranulation and cell adhesion proteins such as fibronectin, vitronectin and fibrin. The mechanism of action is based on the activation of transmembrane receptors of adult mesenchymal stem cells, osteoblasts, fibroblasts, endothelial cells, and epidermal cell lines by the growth factors.

The results from twenty patients who underwent tooth extractions because of root fracture of periodontitis are reported by Anitua et al.⁹ One group received PRP; in five of the ten patients in this group PRP was mixed with autologous bone to prevent tissue collapse. The remaining ten patients were left untreated and served as controls. The epithelialization in all of the cases treated with PRP was complete and significantly better than in areas treated without PRP. Osseous regeneration of mature bone was greater in quantity and quality in the PRP sites. Some limitations of this study include the absence of statistical analysis and the utilization of bone grafts in five out of ten experimental PRP sites that might have contributed to the favorable results as well as the subjective evaluation of soft-tissue healing. More recent evidence to support supplementing bone grafts with PRP was published by Marx in 2004¹⁰.

Despite its clinical acceptance, the scientific evidence for the use of PRP is based on promising case series and case reports. There is little data available to indicate an evidence-based advantage of grafting plus PRP compared to grafting alone.

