4.3 Randomized Extraction Groups

Group 1. Atraumatic extractions followed by saline irrigation and natural healing [CONTROL]

Group 2. Atraumatic extractions followed by Freeze-Dried Bone Allograft (FDBA)/Tri-Calcium Phosphate (TCP) + collaplug

Group 3. Atraumatic extractions followed by FDBA/TCP/Platelet-Rich Plasma (PRP) +collaplug

Group 4. Atraumatic extractions followed by FDBA/TCP/Platelet-Derived Growth Factors (PDGF) + collaplug

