4.7 Grafting Extraction Sockets

After extractions, sockets will be grafted according to each participant's assigned randomization group.

Group-1: Each socket will be irrigated with sterile saline and allowed to heal naturally [control group].

Group-2: Each socket will be grafted with freeze dried bone allograft (FDBA) mixed with Tri-calcium phosphate (TCP) 8:2 ratio; reconstituted with sterile saline.

4.7-2a Irrigate sockets with sterile saline

4.7-2b Pack the graft into each of the study sites using mild pressure achieving complete fill of the sockets.

4.7-2c Trim a 3mm section of collaplug and secure it over the grafted areas with 4.0 Vicryl crossing mattress sutures.

Group 3: Each socket will be grafted with an 8:2 ratio FDBA/TCP graft reconstituted with Platelet Rich Plasma (PRP).

4.7-3a Collect 9-18cc blood sample from the patient via venipuncture prepare the PRP following the Cascade Fibrinet System (Appendix A)

4.7-3b Mix PRP in the FDBA.TCP graft.

4.7-3c Irrigate sockets with sterile saline.

4.7-3d Pack the graft into each of the study sites using mild pressure achieving complete fill of the sockets

4.7-3e Trim a 3mm section of collaplug and secured it over the grafted areas with 4.0 Vicryl crossing mattress sutures.

4.7-3f Once secured in place, the soak the collaplug with PRP.

Group 4: Each socket will be grafted with an 8:2 ratio FDBA/TCP graft reconstituted with recombinant platelet derived growth factor (PDGF).

4.7-4a Irrigate sockets with sterile saline.

4.7-4b Apply PDGF into the sockets completely wetting all socket walls.

4.7-4c Mix PDGF with GEM-21S (product insert Appendix B)

4.7-4d Pack the graft into each of the study sites using mild pressure achieving complete fill of the sockets

4.7-4e Trim a 3mm section of collaplug and secure it over the grafted areas with 4.0 Vicryl crossing mattress sutures.

4.7-4f Once secured in place, soak the collaplug with PDGF.

After completion of procedures the Essix retainer (if used) will be fitted and placed.

A CBCT scan will be made to include images of each study site. Prescriptions for anti-bacterial mouth wash, antibiotics, and pain relief will be provided based on individual patient needs. An ice-pack will be dispensed. Verbal and written home care instructions will be given and the patient will be scheduled for a follow-up appointment.

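### SA-2 labels several contrasts as the growth-factor effect, but only Group 4 v Group 2 isolates enrichment; PRP v plain graft has no planned contrast outside Tukey

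*Combined protocol and SAP*

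**What the plan says.** Hypothesis II (section 2.3) concerns adding growth factors to graft material. SA-2 in section 12.4 is worded "Assess the efficacy of bone grafting with and without enrichment with growth factors", with bone volume as the outcome.

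Sections 4.3 and 4.7 define the arms. Group 1 has no graft and heals naturally. Groups 2, 3 and 4 are all described as receiving an 8:2 FDBA/TCP graft. The Group 2 graft is "mixed with Tri-calcium phosphate (TCP) 8:2 ratio; reconstituted with sterile saline"; Group 3 uses PRP as the liquid and Group 4 uses PDGF.

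For SA-2, section 12.4 plans a four-group mixed-model ANOVA with post-hoc Tukey pairs. It then says that the enrichment effect will be addressed by contrasts that "compare the mean of Group-4 with those of each of the other groups". If the means of Groups 1-3 do not differ significantly, "the combined mean of these three groups will be compared with that of Group-4". No significance level is given for that preliminary test. No contrast of Group 3 with Group 2 is named.

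Section 1.2 says that PRP "consists of growth factors derived from platelets degranulation" and cell adhesion proteins. It identifies the benefit of PRP over grafting alone as a question with little evidence. Section 1.8 describes the PRP graft as enriched.

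**The concern.** An enrichment effect is a difference between an enriched graft and the same graft without enrichment, so Group 2 is the reference. SA-2 gives the enrichment label to contrasts whose comparator has no graft (Group 1), contains another growth-factor product (Group 3), or mixes both with the plain graft (the pool). The pool is also entered on a non-significant test, which is weak evidence that three small groups are alike.

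Two things are at stake. A benefit of grafting, which belongs to Hypothesis I, could be reported as a benefit of growth factors. And PRP against plain graft, which the background names as an open question, is tested only as one of six Tukey pairs.

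**Working it through.** **What each contrast estimates.** Let g be the graft effect, p the added effect of PRP and d the added effect of PDGF, taken as additive. The group means, relative to Group 1, are 0, g, g + p and g + d.

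- Group 4 v 2: (g + d) − g = d
- Group 4 v 1: g + d
- Group 4 v 3: d − p
- Group 4 v pool: (g + d) − (0 + g + g + p)/3 = d + g/3 − p/3

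The pool equals d only if g = p. For example, both could be zero.

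**Inputs.** From section 12.5: 25 effective observations per group (used there as 25 v 75 for SA-1), a medium effect of 0.5 sd, and two-sided 5% tests. My assumptions: a 5% gate, and effective sites treated as independent. Ranges use n = 20 (one site per participant) to n = 27 (the largest effective size in section 12.5).

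**The plan's own figure.** Section 12.5 gives 52% power for SA-2. The noncentral F with four groups, n = 25 and f = 0.25 gives 51.8%, so it reproduces. That is the power of the overall test, not of any enrichment contrast.

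**Contrast power (noncentral t, 96 df at n = 25).** A pairwise contrast has standard error √(2/25) = 0.283 sd, so 0.5 sd has noncentrality 1.77 and power 41.7% (34.5% at n = 20, 44.4% at n = 27). The pooled contrast has standard error √(1/25 + 1/75) = 0.231 sd. Ungated, its power is 57.3% at 0.5 sd, 29.8% at 0.33 sd and 11.0% at 0.17 sd.

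**The gated rule.** Simulated trials with n = 25 and each non-zero effect at 0.5 sd. Percentages are rejection rates except in the gate column.

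| What works | 4 v 2 | 4 v 1 | 4 v 3 | Pool expectation | Gate passes | Pool rejects when used |
|---|---|---|---|---|---|---|
| Nothing | 5% | 5% | 5% | 0 | 95% | 4.9% |
| Graft only | 5% | 42% | 5% | +0.17 sd | 58% | 10.7% |
| PRP only | 5% | 5% | 42% (against Group 4) | −0.17 sd | 58% | 10% (against Group 4) |
| PRP and PDGF, not graft | 42% | 42% | 5% | +0.33 sd | 58% | 29% |
| PDGF only | 42% | 42% | 42% | +0.50 sd | 95% | 57% |

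**Graft only, in more detail.**

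- The gate passes in 66% of trials at n = 20 and 55% at n = 27. The pool then rejects in 9.4% and 11.2%.
- At n = 25 the pool rejects in 0.58 × 10.7% = 6.2% of all trials.
- Leaving Group 4 v 1 aside, the labelled contrasts favour Group 4 in 8.0% of trials, against 5.1% when nothing works.
- The Tukey comparison of Group 2 with Group 1 has 20% power. It is non-significant in 65% of the trials where Group 4 v 1 favours Group 4, so the Tukey table would often fail to show that the graft explains the result.
- With a graft effect of 0.65 or 0.80 sd, Group 4 v 1 rejects in 62% or 80%. The gate passes less often (36% or 17%) and the pool then rejects in 15% or 19%.
- With a gate level of 0.10 or 0.20 the gate passes in 45% or 31%. Rejection when pooled stays near 10.7%, which is 4.8% or 3.3% of all trials.

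**PRP against plain graft.** At 0.5 sd and n = 25, Group 3 v 2 has 20% power through Tukey (critical t 2.61), 42% as an unadjusted planned contrast, and 31% under Holm with Group 4 v 2 if only PRP works.

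**The case against.** The right contrast is already there: Group 4 v 2 is planned unconditionally and Group 3 v 2 is among the Tukey pairs, so no comparison is lost. This stands, and it limits the fault. It does not settle which of up to four labelled contrasts answers SA-2.

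The 42% for Group 4 v 1 is not a false-positive rate; it detects a real difference. That also stands: the error lies in the label. The pool's effect on overall error is modest, at 6.2% of all trials against about 4.8% when nothing works (0.95 × 5%).

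Growth factors may mean PDGF only, since section 12.4 ties enrichment to Group 4. On that reading the PRP point falls away. Sections 1.2 and 1.8 favour the wider reading, and on either one Group 4 v 1 and the pool are not enrichment effects.

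Comparing 20% under Tukey with 42% unadjusted is not like for like. With multiplicity control the fair figure is 31%, a gain of about 11 points.

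Finally, section 4.7 gives Group 4 the same 8:2 graft as Group 2, but step 4.7-4c refers to mixing PDGF with GEM-21S, a product that the Group 2 steps do not mention. If the carriers differ, Group 4 v 2 includes that difference too. Those statements need to be reconciled, but this does not rescue Group 4 v 1 or the pool.

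**Conclusion.** The concern holds and should be fixed. As written, SA-2 can report a graft effect, or a difference between two growth-factor products, as the effect of enrichment. If only the graft works by 0.5 sd, with 25 effective sites per group, Group 4 v 1 is significant in 42% of trials. The pool is used in 58% and rejects in 10.7% of those. If only PRP works, the labelled contrasts tend to point against enrichment.

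These sizes rest on additive effects, a 5% gate that the plan does not state, and the plan's own effective sample size. What each contrast estimates follows from the arm definitions and does not depend on sample size or gate level. The PRP part depends on counting PRP as growth-factor enrichment. The fault is confined to SA-2: the data, the model, the overall F-test and Group 4 v 2 are unaffected.

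**What to change.** In SA-2, name Group 4 minus Group 2 and Group 3 minus Group 2 as the enrichment contrasts. Delete the conditional pooling of Groups 1-3. Leave Group 4 v 1 and Group 4 v 3 in the Tukey set without the enrichment label. State whether multiplicity is controlled across the two enrichment contrasts; Holm is one option, and either choice is acceptable if declared.

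This changes wording only; the model and data stay the same. If PDGF alone works, the pooled test's 57% power is given up for the 42% of Group 4 v 2. Without multiplicity control, the two contrasts have a familywise error of 9.1% when neither product works. With Holm, power at 0.5 sd is 31% for the effective product if only one works, and 35% for each if both do.
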